Adhering to guidelines for safe return to activity/school is a challenge for youth. Lack of adherence can contribute to prolonged recovery and repeat injuries. Youth like Katie who sustain a concussion are predominantly provided with management strategies based on professional consensus Return to Activity (RTA) and Return to School (RTS) protocols, with most referencing the Berlin Consensus Statement (2017). ¹ These protocols were designed for adult athletes ¹ and very little monitoring occurs to inform how or when a child/youth should progress through the stages. It is notable to the reader that the term youth will be applied throughout this document to define our population of interest which includes those between the ages of 10 and 18.

Our research team has made significant advances in the management of concussion in youth by creating evidence-based child-and-youth-specific protocols for RTA and RTS (www.canchild.ca). In evaluating these guidelines, our team found that youth had difficulties following the protocols due to lack of feedback and guidance. Further, results from our community-based study, which included the partnering school board, showed much variation in the implementation of the concussion protocols in youth amateur sport. 4

What is needed now – what will help youth like Katie – is **a comprehensive concussion management platform** that can monitor and evaluate symptoms, real-time activity monitoring that guide youth on how to adjust activity to minimize symptom exacerbation. The aim of this project is to develop a new concussion management platform (Back2Play App), which will be available to youth post-concussion via mobile device. The platform will guide youth through the revised CanChild RTA and RTS Protocols (2018)²; include real-time monitoring of biological variables including heart rate, movement, symptoms, and cognitive activity; as well as incorporate new evidence on the balance of rest and activity from the CIHR funded 'Back to Play' Study.

Research Question

Does a newly developed interactive Back2Play App, available on mobile devices, reduce time to symptom resolution and return to full activity and prevent reinjury 3 months after initial injury in youth aged 10-18 years with concussive injury as compared to usual care?

Hypothesis - We hypothesize that using the mobile health platform (Back2Play App) device will improve adherence to management strategies and will result in quicker recovery (defined as a quicker return to activity and school without symptom exacerbation, minimize development of Post-Concussion Syndrome (PCS) (greater

than 1-month symptom duration post injury) and prevent repeat injuries in the early vulnerable post-concussive period.

This project will occur in three phases; Phase 1: App Development, Phase 2: Usability Testing, and Phase 3; Feasibility RCT. **This application is for Phase 3 of the Back2Play App study.** Phase 1 and 2 were previously approved (#7393). The study will explore whether a newly developed Back2Play App, available on mobile devices, reduces time to symptom resolution and time to return to full activity/school and prevents reinjury within three months of initial injury in youth aged 10-18 years with concussive injury as compared to usual care.

Secondary objectives of this study will be:

☐ To conduct a multicentre Randomized Control Trial (RCT) comparing The
Back2Play App to Usual Care with our partners at Montreal Children's Hospital
(MCH), McMaster Children's Hospital, David Braley Sports Clinic (DBSC) and other
clinics and community partners
☐ To evaluate through survey and interview, the perceptions of The Back2Play App from
parents and youth.
☐ To explore commercialization of the new product.

Novelty and Significance of the Research - Most existing concussion management apps aim to provide education and some method for recording and tracking symptoms. These apps are information dense, lack user interaction and fail to integrate child/youth patterns of activity with symptom exacerbation to provide guidance about RTA and RTS based on evidence-based guidelines. By creating The Back2Play App that incorporates and streamlines key aspects of concussion management and monitoring, we will provide youth and their families with more autonomy and understanding of their recovery trajectories, with the goal of increasing overall adherence.

Return to activity/school is about (i) having adequate recovery time to eliminate or decrease symptoms and (ii) adhering to guidelines that gradually increase the amount and level of physical and mental activity to control symptom exacerbation ^{1, 5-9}. Activity monitoring through accelerometry and symptom tracking through the Post-Concussion Symptom Scale (PCSS)¹⁰, combined with management protocols that give parameters for these would provide individualized feedback that is time sensitive. This mobile application would represent advances in individual data collection and adherence monitoring, while suggesting alternate activities based on clinically developed RTA/RTS Guidelines. The Back2Play App will be tested and refined with youth with concussion providing a realistic measure of clinical utility as well as desirability and approval by youth. The App includes a machine learning component that is currently observatory in nature, and for the purposes of the current study, will not be used to provide feedback to users.

Development of such techniques could provide insight as to how using these new methods may be incorporated into return to activity decision-making, which at present is subjectively decided by coaches, clinicians and parents. We believe these new methods of evaluation will provide not only the foundation of future research, but also information with immediate clinical utility. **The Back2Play App is not meant to replace medical management but to be a safe adjunct. Long-term, we aim to change the overall management and outcomes of childhood concussion.** The Back2Play App will have the potential to alter the current landscape of pediatric concussion management and research.

This ethics application builds on existing work and previously approved phases (#7393) from our 3-phase project:

Phase 1: We developed The Back2Play App in English and French. The App can monitor concussion symptoms, physical and cognitive activity level as well as the stage of the RTA/RTS Guidelines to assist in managing concussion recovery in children and youth. During this phase, we had 2 participants, youth with concussion, participate in User Experience testing sessions at the Institute of Applied Health Sciences at McMaster University. User Experience testing sessions are important in the technology industry because they assess the customer's response to a prototype of a product. We asked participants to use the Back2Play App on an iPhone and Apple Watch for 1 week and give us feedback on our App. Following User Experience, the App development team made improvements (extending survey times, language, use of colours) to ensure functionality and ease of use.

Phase 2: In this phase we pilot tested the The Back2Play App with youth. Youth were recruited from the Hamilton Wentworth Catholic District School Board (HWCDSB), McMaster Children's Hospital, Montreal Children's Hospital and Concussion clinics within the community. Unfortunately, because of COVID-19 restrictions the number of youth with concussions was low and a total of 17 participants were enrolled in this portion of the study. The main goal of the pilot was to test the App's content and usability at home and school with youth and get feedback to redevelop it. Overall youth reported a high satisfaction rate with The App. The System Usability Scale (SUS), which is a 10 item questionnaire administered to participants was used due to it's ease in evaluating software. On the SUS, a mean of 70% and median of 75% was achieved. The SUS reports that 68% is an average score and anything below that may require redevelopment. Youth also gave qualitative feedback on timing of surveys and troubleshooting issues which are currently being updated in the App.

We were also collecting data to develop machine learning algorithms that will be embedded within the Back2Play App prior to Stage 3. This algorithm will be tested and further trained to understand what stage of RTA/RTS the youth is in based on their symptom level, heart rate and movement data. A support vector machine classification algorithm was built using data from the pilot. Because enrollment was so low, the stages of guidelines were collapsed and the model currently predicts Stage 2, 3, 4 and 5 of RTA and 2, 3, and 4 of RTS. The architecture of this algorithm is sound but the predictive capabilities need more work, thus the algorithm will sit on the phone in the background and predictions will be sent directly to the B2P database. No information from the

algorithm will be shared with participants or used by The App to provide guidance through notifications.

Phase 3: The goal of Phase 3 is to conduct an RCT with our partners (Montreal Children's Hospital, McMaster Children's Hospital) comparing the effectiveness of the innovative Back2Play App versus Usual Care. We will assess whether The Back2Play App shortens the duration and intensity of post-concussion symptoms and prevents repeat injury in youth post-concussion. To do so we will evaluate:

- 1) Total symptoms, symptom severity and duration of symptoms.
- 2) Time to symptom resolution.
- 3) Risk for repeat head injuries within three months of initial injury.

2. BACKGROUND

Concussion, also referred to as mild traumatic brain injury (MTBI), is a major public health concern. Despite increased recognition of the serious health impacts of concussion, the number of injuries is rising in both Canada and the United States. ¹ The presentation of symptoms after a concussion can have a significant impact on a youth's participation in daily life, including at school and in sport.

Concussion is a common child/youth health problem. In Canada, an estimated 15,970 patients presented to emergency departments (ED) with a sport-related head injury, including concussion, in 2011/12. Among children and youth aged 5-18, there was a reported 42-47% increase in the proportion of head injuries relative to all other injuries in football, soccer and ice hockey between 2004 and 2014. The actual number of concussion incidents is believed to be even higher given that many injuries go unreported. In a prospective Canadian study, Echlin *et al.* ¹³ observed an incidence of 21.5 concussions per 100 athlete exposures.

Concussion in children presents with a range of severity and results in short and long-term physical (e.g., headache, nausea, balance problems, dizziness, visual problems, fatigue), cognitive (e.g., feeling mentally 'foggy', difficulty concentrating or remembering), emotional/ behavioural (e.g., irritability, sadness, nervousness, anxiety) and sleep dysregulation sequelae which are collectively known as Post-Concussion Syndrome (PCS). 14-16 These symptoms are usually aggravated by physical and cognitive exertion if the child/youth has not fully recovered. Barlow *et al.* 17 note that diagnostic criteria for PCS may not vary in the type but in number and/or duration of symptoms present. This epidemiologic study from Alberta, Canada 17 confirmed that 59% of children/youth continued to be symptomatic one-month post-injury, 14% of children remained symptomatic three months post-injury and 2.3% were still symptomatic at one year. These results are congruent with data collected at the Acquired Brain Injury (ABI) Follow-Up Clinic at McMaster Children's Hospital (MCH). Here, 47% of children/youth still had 4 Back2Play App: Protocol Version 3 June 1 2022

symptoms or more at 1 month post concussive injury. There is now a prediction risk score for PCS^{18} which helps clinicians determine at presentation which children will go onto have PCS or symptoms past one month. All children/youth still must be monitored to determine if their symptoms resolve early or if they are among the 50% of children/youth at risk for symptoms lasting greater than one month, or one of the 13% that are symptomatic beyond three months post-injury. There is now a growing body of evidence to show that with education, comprehensive assessment and rehabilitation, symptom resolution may occur sooner and secondary problems like depression and school failure can be prevented. 19

Multiple concussions are common in the pediatric population

Swaine et al.²⁰ found that concussed children are twice as likely to receive a subsequent head injury within 12 months. Moreover, more than 30% of high school athletes have been shown to sustain multiple head injuries.²¹⁻²² Greater than 34% of children who received service at the ABI Follow-Up Clinic at MCH had experienced multiple concussions, with 17% experiencing three or more injuries.

Children who have sustained multiple concussions often have prolonged and severe symptoms including learning difficulties, behavioural problems, debilitating headaches, visual problems, and impaired memory. 23-25 Concussion often results in substantial long-term cognitive and behavioural disturbances that can have significant impact on the quality of life of individuals. 26-27 Our own research supports these findings as we found that children with mild injuries had decreased quality of life and neuropsychological impairment at five years post-injury compared to norms for age. 28 This evidence, in combination with the growing body of knowledge surrounding chronic traumatic encephalopathy (CTE) (where degeneration has been demonstrated in the brains of athletes who have had multiple concussions, some as early as 18 years of age 29-30), commands us to prevent these repetitive injuries even though we may not yet fully understand the mechanisms and individual propensity to this debilitating condition.

Current approaches to concussion management have limitations

The Berlin Consensus 2016 Concussion in Sport Group (CISG)¹, which recently updated The Zurich Consensus³¹, has provided guidelines for return to play for adult athletes which major sport and prevention institutions are readily adopting. These consensus statements were originally designed to provide general recommendations for the management of sport concussion in adults, with the pediatric population being considered in subsequent more recent versions.

While children and youth do present with similar post-concussion symptoms as adults, several investigators and The Berlin Consensus ¹ have noted the need for a more conservative approach for their concussion management due to the unique physiological

make-up among the pediatric patients. ³²⁻³⁴The CanChild Protocols for Concussion Management for children and youth 5-18 years ³⁵⁻³⁷ used in this proposed study were developed with reference to the consensus statements. ¹ The CanChild protocols highlight the need for graduated RTA and RTS management strategies that reflect the pattern of recovery that is unique to each child/youth. Focusing on an individual's unique pattern of recovery may better reflect the complicated course of healing that requires more than a 'one size fits all' set of recommendations.

There are five stages in the CanChild RTS protocol² and six stages in the RTA protocol.² In these protocols, all children/youth are advised that there can be no high-level physical activity or contact sport while symptoms are present. However, 'rest' does not equate to social isolation or sensory deprivation. Daily activities that can be tolerated for each stage of recovery, without symptom exacerbation, are identified in the Activity Suggestions supplement that accompany the protocols, both of which are available on the CanChild website.² Families often find it difficult to gauge the appropriate amount of activity, including cognitive effort, for their child/youth's stage of recovery. The therapeutic goal in managing concussion recovery is to find the individual's level of cognitive and physical exertion that promotes healing which is the focus of our proposed Back2Play App. This graded approach was highlighted in a recent systematic review comparing the difference in concussion management in children/youth versus adults that was part of the CISG 2016 meeting in Berlin.¹ Importantly, this systematic review identified the need for an effective pediatric specific concussion management protocol.³⁸

Current Concussion Management Platforms

Very little research exists on the use of concussion management platforms for treatment/prevention. A total of 5 articles ³⁹⁻⁴³ were retrieved from the PubMed database. As noted earlier, the main goal of these apps was to provide education and some method for recording and tracking symptoms. The Self-Monitoring Activity-Restriction and Relaxation Treatment - SMART provides recommendations for individualized symptom management, activity restrictions, guidance, stress management, relaxation and problem-solving skills following concussion. The Brain 101: The Concussion Playbook is purely a web-based education tool designed for sports-related concussion training. All studies had small sample sizes.

Back2Play App

The Back2Play App was developed in phase 1 of this project, to capture self reported symptoms and stages of recovery that youth indicate by filling in daily surveys and combine these with biological/activity data to track progress and give feedback about their recovery from concussion based from currently existing published guidelines. Accelerometry and heart rate data are collected through the Apple watch and sent to the API as well so that real time notifications can be given that may help youth adhere to the RTA/RTS guidelines. All notifications are based on published evidence-based guidelines used in clinical practice.

(https://canchild.ca/system/tenon/assets/attachments/000/002/642/original/Return_to_Activit y_Guideline_WEB_1_Reference.pdf).

Rules, precedingly referred to as 'business rules', were developed for in App notifications that follow the guidance of the RTA/RTS protocols for progression through the stages (Appendix 1.1) Symptoms, self reported stages and activities are measured daily in the morning, afternoon and evening. A summary of these surveys is found in appendix 1.2. The home screen of the App (appendix 1.3) summarizes the next survey time, current stage of return to school and activity the youth is reporting that day and the activity minute goals (based on their stage of recovery) and how many activity minutes are completed. Icons at the bottom direct users to 1) a summary page that will show this information as well as a graph of their current symptoms, 2) a charts page which has several graphs of their progress (symptoms, stages, heart rate and activity minutes), 3) resources including the CanChild guidelines for concussion recovery, symptom strata (or the type of recovery pattern they may be following), the playsafe cards for individual sport specific strategies and a list of activity suggestions for each stage of recovery and 4) a contact us page which gives the Research Team [contact] and Principal investigator contact info as well as a form for troubleshooting help. When youth fill out the surveys, if 2 or more symptoms are worse, a pop up option of texting or emailing the participant's parent appears (appendix 1.3) Notifications are also sent to youth who exceed their activity goals and the Back2Play App will send a cautionary message "You are doing too much!" if their heart rate goes above 180. Encouraging notifications are also programmed with business rules if participants stay in the same stage for extended periods or if their symptoms get worst.

A complimentary App was developed by [name] of our investigator team. This Brain Games App was designed to screen some typical neurocognitive functions affected by concussion. There are 5 "games" that take about 10 minutes to complete. These include 1)

finger-tapping, 2) divided attention, 3) memory for designs, 4) tracing and 5) face match. An 'in App notification' is triggered by the youth recording a progression in their RTS stage. "Let's do a brain teaser! Sign into The Back2Play Brain Games App for your brain game then complete your symptom survey!" If the challenging tasks result in increased symptoms, The App notifies them "The brain game can be hard, stay at this stage if you need too!"

These tasks may give the user some indication of readiness to move on in their recovery.

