7. INTERVENTIONS

Participants randomized to the control group will be provided Usual Care which often is some type of gradual return guidelines the practice (ED, General Practitioner) subscribes to. These are usually provided in a paper format for the patient to take home. Participants in the Usual Care group will complete symptom surveys every 24 hours via REDCap. The Back2Play App requests symptom surveys be done 3 times daily (quickly done on the watch or phone). The Back2play App also asks users to go to the BrainGames App when participants indicate they are ready to progress to the next stage of RTS in the guidelines. In The BrainGames App they can complete 5 neuropsychological tasks that provide feedback about their readiness to progress. These tasks are not available for those in the Usual Care group.

Surveys about cognitive and physical activities engaged in as well as the participants self-rating of cognitive activity level (1-5) and stage of recovery (1-5/6) are done on a daily basis by both groups.

Participants who have been randomized to the App group will be asked to:

- Download The Back2Play App and The B2P BrainGames App on their iPhone and the Apple Watch provided either at the ED or at a scheduled baseline visit (within 2 days of concussion).
- Pair the Apple Watch to their iPhone and wear an Apple Watch for the duration of the study.
- Complete the initial post-concussion symptom survey on the App with the Research Assistant and receive orientation to The Back2Play App.
- Complete 3 symptom surveys per day on The Back2Play App (Morning, Afternoon and Evening) and daily surveys about cognitive and physical activities as well as self-rating of participants' own cognitive level of activity and stage of concussion recovery until 2 days following symptom resolution.
- Complete games on the B2P BrainGames App (i.e. matching games) which are suggested whenever the participant moves up a stage in RTS Protocol.
- Attend a Zoom Follow Up meeting 2 days after symptom resolution or after a maximum of 3 months of using The App. Here, we will ask participants questions about their perceptions of how well The App guided them through their recovery. Did they agree with classifications and notifications, did they understand the guidelines as well as questions about any other interventions they may have received. This Zoom visit will be recorded and saved to a secure, password encrypted study computer.

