Page 1: Current symptoms - App generates what was reported yesterday - Global "How are you" question Page 2: New Symptoms	"Please select what cognitive activities you have been doing today" 1. School work 2. Test/Quiz 3. Study 4. Socialize with friends 5. Text/phone friends 6. Use iPhone Apps i.e. Snapchat 7. Play on the iPad 8. Watch T.V. 9. Watch a YouTube video 10. Watch a movie 11. Play video games 12. Play a board game 13. Read/Re-read a book 14. Listen to music 15. Puzzles 16. Other	"Please rate 1-5 what you've been doing today" Cognitive Scale "What Stage of the RTS protocol are you in? Select: 1, 2, 3, 4, 5" "What Stage of the RTA protocol are you in? Select: 1, 2, 3, 4, 5" "What physical activities did you do today?" 1. Jog 2. Bike 3. Hike 4. Swim 5. Stretch/Yoga 6. Skate 7. Play Catch 8. Passing, shooting drills 9. Dribbling/Stickhandling 10. Throwing/Passing drills 11. Sports-specific drills 12. Basketball 13. Soccer 14. Football 15. Hockey 16. Rugby 17. Resistance training 18. Track and Field 19. Squash/Tennis 20. Other "Daily Symptom survey"

Daily Symptom survey

Page 1: Current symptoms

- App generates what was reported yesterday
- Global "How are you" question

Page 2: New Symptoms

"Please select what cognitive activities you have been doing today"

- 1. School work
- 2. Test/Quiz
- 3. Study
- 4. Socialize with friends
- 5. Text/phone friends
- 6. Use iPhone Apps i.e. Snapchat
- 7. Play on the iPad
- 8. Watch T.V.
- 9. Watch YouTube videos
- 10. Watch a movie
- 11. Play video games
- 12. Play a board game
- 13. Read/Re-read a book
- 14. Listen to music
- 15. Puzzles
- 16. Other

"Please rate 1-5 what you've been doing today"

Cognitive Scale

"What Stage of the RTS protocol are you in? Select: 1, 2, 3, 4, 5"

"What Stage of the RTA protocol are you in? Select: 1, 2, 3, 4, 5"

"What physical activities did you do today?"

- 1. Run
- 2. Jog
- 3. Bike
- 4. Hike
- 5. Swim
- 6. Stretch/Yoga
- 7. Skate
- 8. Play Catch
- 9. Jumping jacks/Burpees
- 10. Passing, shooting drills
- 11. Dribbling/Stickhandling
- 12. Throwing/Passing drills
- 13. Sports-specific drills
- 14. Basketball
- 15. Soccer
- 16. Football
- 17. Hockey
- 18. Rugby
- 19. Resistance training
- 20. Track and Field
- 21. Squash/Tennis
- 22. Other

"Daily Symptom survey"

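### At return-to-school stage progressions the App suggests possibly symptom-raising tasks and then asks for the symptom survey; Usual Care has no such tasks, and no rule keeps post-game answers out of the symptom outcomes

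*Combined protocol and SAP*

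**What the plan says.** Section 2 (Background, Back2Play App) describes a companion Brain Games App with five neurocognitive tasks lasting about 10 minutes. The trigger is stated: "An 'in App notification' is triggered by the youth recording a progression in their RTS stage". The message puts the game first and the survey second: "Sign into The Back2Play Brain Games App for your brain game then complete your symptom survey". The protocol allows for a reaction to the tasks: "If the challenging tasks result in increased symptoms, The App notifies them", with advice that the youth may stay at the present stage.

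Section 7 (Interventions) says of the games that they are ones "which are suggested whenever the participant moves up a stage in RTS Protocol", and of the control arm: "These tasks are not available for those in the Usual Care group". Usual Care youth answer a symptom survey sent by email every 24 hours, with no task before it.

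Section 8 (Design) makes time from injury to symptom resolution a primary outcome and symptom frequency a secondary one. It states that the 22-item scale was modified to record whether a symptom is present, not how severe it is. Section 9.5 analyses time to resolution with survival curves and Cox regression. Neither section mentions surveys answered after a game.

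**The concern.** A symptom outcome should be read under the same conditions in both arms. Here, on certain days, the App arm may be read just after a cognitive challenge, and Usual Care never is. Section 2 itself notes that cognitive exertion usually aggravates symptoms in a youth who has not fully recovered.

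Time to resolution depends on the few reports around the first symptom-free day, and a presence-only scale gives a mild, short-lived headache the same weight as a lasting one. A reaction to a test could then be recorded as continuing concussion. That would lengthen recorded recovery in the App arm and could hide part of a real benefit.

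**Working it through.** **What the plan fixes for each arm**

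| Item | App | Usual Care | Source |
|---|---|---|---|
| Cognitive tasks | Suggested at each RTS step up | Not available | Sections 2, 7 |
| Order on those days | Game, then survey | Survey only | Sections 2, 7 |
| Scheduled symptom surveys | 3 per day | 1 per 24 hours | Sections 7, 8 |
| Rule for post-game answers | None | Not applicable | Sections 8, 9.5 |

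The arm difference follows from carrying out the plan as written.

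**How often it can happen.** Section 2 states: "There are five stages in the CanChild RTS protocol". Five stages allow 5 − 1 = 4 upward steps if none is repeated, so at most 4 prompted post-game surveys per App youth and 0 in Usual Care. As a share of scheduled App surveys:

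- over 7 days: 4 / (3 × 7) = 19%
- over 28 days: 4 / (3 × 28) = 4.8%
- over 90 days: 4 / (3 × 90) = 1.5%

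**When it can change the primary outcome.** If the youth already has a symptom that day, the record is symptomatic with or without the game, and time to resolution does not move. A new post-game symptom could still raise symptom frequency. Time to resolution moves only if the post-game survey falls on what would have been a symptom-free report that counts toward resolution.

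**Size.** The plan gives no figure for this effect, so the only benchmark is the 10% reduction in recovery time that section 3 calls clinically significant. To turn that into days, I fitted a Weibull curve, S(t) = exp[−(t/λ)^k], to the cohort figures in section 2: 59% symptomatic at one month (30 days) and 14% at three months (90 days).

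- k = ln[ln(1/0.14) / ln(1/0.59)] / ln(90/30) = 1.197
- λ = 30 / [ln(1/0.59)]^(1/k) = 51.2 days
- median = λ × (ln 2)^(1/k) = 37.7 days
- 10% of the median = 3.8 days

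Mean shift = (share of App youth affected) × (delay in an affected youth). Both inputs are assumptions. The delay is 1 day if the next day's report is clear, and 1 + 2 = 3 days if resolution must also hold for two further days. The share is set at 10% to 50%.

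| Share affected | 1-day delay | 3-day delay |
|---|---|---|
| 10% | 0.1 day (3% of 3.77) | 0.3 day (8%) |
| 25% | 0.25 day (7%) | 0.75 day (20%) |
| 50% | 0.5 day (13%) | 1.5 days (40%) |

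Setting a mean shift against a fraction of a median is approximate. Section 2 also cites about 50% symptomatic beyond one month. That would put the median near 30 days and the benchmark near 3 days, and the top of the range would become 1.5 / 3 = 50%.

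**Sample size.** The plan's numbers rest on repeat head injury (128 / (1 − 0.20) = 160) and are not affected.

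**The case against.** The strongest reply is that this is narrow. The prompt comes only at RTS progressions, the games are suggested and not required, and the protocol says only that symptoms may increase. Youth can progress while symptomatic, since Appendix 1.1 prompts moves after 7 and 14 days in a stage, so many post-game surveys will not touch the primary outcome. The likely bias is against the App, so it would not create a false claim of benefit. The lack of a definition of symptom resolution and the three-a-day versus daily schedule are larger problems in the same outcome. All of this stands, and it limits the weight of the point without removing it.

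It can also be said that the game is part of the intervention, so its effects belong in the comparison. That holds for lasting effects. A brief reaction to a 10-minute task is not the recovery that the outcome is meant to measure, and the fix leaves the game in place.

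A reader might infer more than the documents support:

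- *That App symptom data in general follow a provocation.* They do not; at most 4 surveys per youth are involved if no stage is repeated.
- *That the post-game survey is always the evening one.* From Stage 2, Appendix 1.2 does put the stage question ("What Stage of the RTS protocol are you in? Select: 1, 2, 3, 4, 5") and a closing symptom survey in the evening form. In Stage 1 the stage question is in the morning form, so this reading covers at most 3 of the 4 steps. Section 2 does not say which survey the message means.
- *That the artefact could equal much or all of the effect of interest because one youth's delay may be 1 to 3 days.* One youth's delay must first be multiplied by the share of youth affected.
- *That setting off the in-App caution rules in Appendix 1.1 is itself outcome bias.* Those rules are feedback and form part of the intervention.

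**Conclusion.** The point holds, within limits. At RTS progressions the plan allows symptom readings taken after a cognitive task in the App arm only, and nothing keeps those readings out of a primary and a secondary outcome. That much rests on the text alone.

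The direction is probably against the App, on the premise that the games sometimes raise symptoms, which the protocol foresees but does not quantify. The size cannot be derived from the documents. The range of 0.1 to 1.5 days, or about 3% to 40% of the effect of interest, rests on the assumed 10% to 50% affected, the assumed 1- to 3-day delay and the fitted 38-day median. This is a worthwhile, inexpensive improvement and does not call the trial into question.

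**What to change.** 1. Have the App collect the symptom survey used for outcomes before it sends the Brain Games prompt.
2. Record any post-game symptom check as a separate, time-stamped and flagged item, used only for in-App feedback.
3. State in sections 8 and 9.5 that post-game checks do not count toward time to symptom resolution or symptom frequency.
4. Describe the trigger in one way. Section 2 says after a progression is recorded; section 7 says both when the youth indicates readiness and whenever the youth moves up.

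The cost is one App sequencing or flag change, a sentence in each section, and one extra short item on up to 4 days per App youth. The sample size and the game itself are unchanged. A once-daily schedule common to both arms would not be enough unless that reading must precede any game. Substituting the same day's morning survey is not a sound alternative. It fails for the Stage 1 to 2 step, where the stage is asked in the morning, and it adds a possible time-of-day difference from Usual Care, whose reporting time is not stated.
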